Objective 1 (Primary): Evaluate whether administration of THC-containing cannabis (versus placebo cannabis) subsequently influences self-administration patterns (time to first self-administration, amount consumed, puffing topography characteristics) of tobacco cigarettes or e-cigarettes.

Objective 2 (Primary): Evaluate whether administration of THC-containing cannabis (versus placebo cannabis) subsequently influences the acute effects (e.g., subjective effects) of tobacco cigarettes or e-cigarettes, nicotine withdrawal symptoms, or craving.

Objective 3 (Secondary): Evaluate whether administration of THC-containing cannabis (versus placebo cannabis) subsequently influences vital signs (e.g., heart rate, blood pressure).

Objective 4 (Secondary): Evaluate whether administration of THC-containing cannabis (versus placebo cannabis) subsequently influences cognitive performance.

3. Background (briefly describe pre-clinical and clinical data, current experience with procedures, drug or device, and any other relevant information to justify the research)

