To date, only two human laboratory studies have evaluated pharmacological and behavioral mechanisms of CT-PSU. In the first study (Penetar et al., 2005), nicotine was administered via a transdermal patch four hours before smoking a cannabis joint. Nicotine did not alter plasma levels of THC; however, it did enhance cannabis-related increases in heart rate, subject ratings of "stimulated," and scores on the amphetamine scale of the Addiction Research Center Inventory. A second study reported that, compared to blunts, cannabis administered in joints produced greater plasma THC levels and subjective ratings of intoxication, strength and quality; however, lower THC plasma levels after blunt administration was attributed to a procedural limitation in that participants had difficulty drawing smoke from the blunts compared to the joints (Cooper and Haney, 2009). Overall, results from these studies suggest that nicotine may enhance some physiological and subjective effects of cannabis, but results are limited by their use of only a single nicotine dose. Prior research has also yet to examine a key CT-PSU behavior known as "chasing" in which users administer nicotine/tobacco after using cannabis, in an attempt to boost or extend their high. Notably, survey data collected to inform the present clinical research study indicated approximately half of the participants who endorsed recent use of both cannabis and tobacco had engaged previously in "chasing behavior," most commonly with conventional cigarettes or e-cigarettes. The present study seeks to evaluate the impact of acute smoked cannabis effects on nicotine/tobacco self-administration "chasing" behavior in current nicotine/tobacco users. Though nicotine/tobacco "chasing" has been previously reported, controlled studies have not been conducted to elucidate whether pre-exposure to cannabis actually alters nicotine/tobacco use patterns or reinforcement among current, nicotine-tolerant smokers/e-cig user, or whether there are differential changes based on nicotine dose or product type (i.e. tobacco cigarettes vs. electronic cigarettes). This research will be a critical first step towards elucidating the underlying mechanisms responsible for CT-PSU which ultimately may improve treatment outcomes for those with disordered use of cannabis and tobacco products

4. Study Procedures

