- a. Study design, including the sequence and timing of study procedures (distinguish research procedures from those that are part of routine care).

Protocol Overview. The proposed study will be conducted at the Johns Hopkins Behavioral Pharmacology Research Unit (BPRU). All participants will be healthy adult volunteers who are regular nicotine/tobacco users, and have prior experience with cannabis use. All procedures will be for research purposes.

Participants will complete seven outpatient experimental test sessions (see table below; completed in a randomized order), under double-blind conditions, in which they will first self-administer smoked cannabis (containing 10mg THC, 25mg THC or placebo), followed by access to their preferred brand of tobacco cigarette or a commercial e-cigarette device (e.g. JUUL) containing a 3% or a 5% nicotine solution for *ad libitum* self-administration. The dose of active cannabis will be determined based on the frequency of cannabis use prior to study participation. Individuals who report using cannabis >2 times per week on average in the 3 months prior to the study will be given an active cannabis dose of 25mg THC and participants reporting cannabis use ≤2 times per week on average will be given an active cannabis dose of 10mg THC. Prior research in our lab indicates that these doses will produce a moderate drug effect across all study participants. There will also be one condition in which participants smoke active cannabis and both cigarette and e-cigarette use will be prohibited during the test session. The seven experimental sessions will consist of:

- 1) Smoked cannabis containing 10mg or 25mg THC + No nicotine/tobacco
- 2) Smoked cannabis containing 10mg or 25mg THC + *ad-libitum* use of preferred brand cigarettes

Date: July 15, 2022

Principal Investigator: [name]

Application Number: IRB00220975

- 3) Smoked cannabis containing 10mg or 25mg THC + ad-libitum use of low nicotine content E-Cig (3% nicotine JUUL)
- 4) Smoked cannabis containing 10mg or 25mg THC + ad-libitum use of high nicotine content E-Cig (5% nicotine JUUL)
- 5) Smoked placebo cannabis + ad-libitum use of preferred brand cigarettes
- 6) Smoked placebo cannabis + ad-libitum use of low nicotine content E-Cig (3% nicotine JUUL)
- 7) Smoked placebo cannabis + ad-libitum use of high nicotine content E-Cig (5% nicotine JUUL)

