Following cannabis exposure, participants will be free to self-administer the assigned nicotine/tobacco product for that session *ad-libitum* (i.e., at their own pace) over the next 5 hours. Conventional cigarettes available for study participants will be their preferred brand of cigarettes and will be purchased by study staff from a retail tobacco outlet. For the e-cigarette study conditions, participants will be provided with the popular, commercially-available, pod-style e-cigarette called the JUUL. JUUL pods contain tobacco-flavored “e-juice” and come in 2 different nicotine concentrations or “strengths” that are designated as either a low (3%; 35mg/mL) or high (5%; 59mg/mL). All cannabis and nicotine/tobacco administration will occur in a specially ventilated room located within the BPRU designed for the administration of combusted/inhaled drug products.

Date: July 15, 2022

Principal Investigator: [name]

Application Number: IRB00220975

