Primary outcome variable is the amount of nicotine used (determined by total volume of cigarette smoke or JUUL vapor inhaled) after cannabis exposure in each session. We hypothesize that exposure to active cannabis will result in greater nicotine use compared with placebo cannabis.

b. Secondary outcome variables.

Secondary outcome variables include other nicotine use behaviors (amount self-administered and puff topography outcomes), subjective drug effect ratings, cognitive and psychomotor performance, and vital signs (HR, BP). We hypothesize that nicotine use will increase subjective drug effect ratings and decrease cognitive performance after exposure to active cannabis compared with the experimental session in which no nicotine/tobacco products are consumed. We also expect that active cannabis will increase self-reported drug effects compared with placebo cannabis.

c. Statistical plan including sample size justification and interim data analysis.

The proposed sample size of 40 study completers was estimated based on limited prior studies. One study found significant effects of transdermal nicotine and smoked cannabis on subjective drug effects with a sample size of N=20, suggesting that the proposed sample size for this study is adequate to detect interactive effects of nicotine and cannabis on subjective drug effects using a within subjects design (Penetar et al., 2005). Evaluation of pharmacodynamic drug effects using a within-subjects design reduces variability across dose administration sessions and significantly increases statistical power to detect differences on the proposed study outcomes. However, because we have a greater number of dose conditions, and because a primary outcome is amount of drug self-administration rather than self-reported drug effects, we expect the need for a greater sample size in this study.

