Initial data analyses will examine whether study completers differ from non-completers with regard to demographic or cannabis use variables. This will inform the generality of the results. We will also examine the data for missing values. When missing data are found in self-report measures we will impute scores by averaging the closest pre and post values when applicable, otherwise missing data will be treated as missing in analyses. Missing data is expected to be rare given that all assessments are conducted via computer and individual items cannot be skipped. However, it is possible that a time point could be missed due to severe drug effects. Data will be evaluated for normal distribution, skewness, kurtosis and appropriate modifications will be made for data that is not normally distributed. All hypothesis tests will be two-sided; α will be set at 0.05. Nicotine/tobacco self-administration data will be analyzed using 2-tailed t-tests comparing the consumption of each nicotine/tobacco product after active versus placebo cannabis pre-treatment. Additional planned comparisons will then be conducted to compare consumption of 3% versus 5% nicotine E-Cig use following active cannabis. Secondary analyses will be conducted using repeated-measures multiple regression to evaluate the effects of nicotine/tobacco product type (None, conventional cigarette, low dose E-Cig, and high dose E-cig) and time as within-subjects factors on subjective drug effect ratings, cardiovascular effects, craving, and cognitive performance effects during sessions in which active (10mg or 25mg THC) cannabis was administered. If sufficient variability in pre-study cannabis use exists in our final study sample, we will conduct exploratory analyses comparing less frequent vs heavy (e.g. daily) cannabis users on primary and secondary outcomes.

d. Early stopping rules.

The study will be stopped if new information is learned that indicates a serious risk to study participants.

7. Risks

a. Medical risks, listing all procedures, their major and minor risks and expected frequency.

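### The only planned 3% versus 5% consumption comparison uses active-cannabis sessions alone, so it cannot show whether cannabis changes the strength effect; a lesser gap is that the three primary t-tests have no stated success rule

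*Combined protocol and SAP*

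**What the plan says.** Section 3 (Background) lists, among matters that controlled studies have not settled, "whether there are differential changes based on nicotine dose or product type". Section 4a supplies the sessions to examine this. Cigarettes, the 3% e-cigarette and the 5% e-cigarette each have one active-cannabis session (2, 3 and 4) and one placebo-cannabis session (5, 6 and 7).

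Study Statistics, part a, makes total inhaled volume the primary outcome and states one directional hypothesis, not divided by product: "We hypothesize that exposure to active cannabis will result in greater nicotine use compared with placebo cannabis". Part c tests it with "2-tailed t-tests comparing the consumption of each nicotine/tobacco product after active versus placebo cannabis pre-treatment". The error rate is set once: "All hypothesis tests will be two-sided; α will be set at 0.05". The plan then adds: "Additional planned comparisons will then be conducted to compare consumption of 3% versus 5% nicotine E-Cig use following active cannabis".

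The repeated-measures regression that has product type as a factor is confined to active-cannabis sessions. Its listed outcomes are subjective, cardiovascular, craving and cognitive, not consumption. Part c gives no multiplicity adjustment, test order or success criterion.

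**The concern.** The main issue is the strength comparison. To learn whether the effect of cannabis on use depends on nicotine strength, one must compare the active-minus-placebo change at 3% with the same change at 5%. No planned consumption analysis does this, although the data will exist. A difference between strengths after active cannabis mixes two things: any difference that would exist without THC, and any change that cannabis makes to it. Section 6a says that participants can titrate nicotine, the liquids are 35 and 59 mg/mL, and the outcome is volume, so the first component may well not be zero. A significant result could then be taken as a cannabis-by-dose finding when it shows only that more of the weaker liquid is inhaled.

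The lesser issue is the primary claim. Three p-values bear on one hypothesis, and the plan does not say which pattern supports it. If only the 5% product is significant, the claim could be reported either way, by a rule chosen after the results are known.

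**Working it through.** **The plan's own figure.** The 40 completers cannot be reproduced, because no effect size, SD or power is given. For orientation, a paired t-test with n = 40 (39 df) at two-sided 0.05 has 80% power for a standardised paired difference of 0.454. The text does not say that the t-tests are paired. I take them as paired because the design is within-subject.

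**What each comparison estimates.** Let mean log volume be m for placebo/5%, m + s for placebo/3%, m + c for active/5%, and m + s + c − d for active/3%. Here s is the strength effect without THC, c the cannabis effect at 5%, and d the amount by which the cannabis effect at 5% exceeds that at 3%.

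- Active sessions only, 3% minus 5%: (m + s + c − d) − (m + c) = s − d. The two parts cannot be separated.
- (Active − placebo at 5%) − (active − placebo at 3%): c − (c − d) = d. The strength effect cancels.

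**How easily s alone gives significance.** With d = 0 and n = 40, an assumed strength difference of 0.3 or 0.5 paired SD makes the active-only test significant with probability 46% or 87% (noncentral t). In terms of titration, if nicotine per unit of vapour is proportional to liquid concentration (an assumption), full compensation means 59/35 = 1.69 times the volume at 3%. A quarter of that on the log scale is 1.69^0.25 = 1.14, and half is 1.69^0.5 = 1.30. I simulated lognormal volumes with no cannabis effect: between-person log SD 0.5–0.8, session log SD 0.2–0.5, and participant-by-cannabis and participant-by-strength log SD 0.15, all assumed. The active-only test was significant in 12–61% of trials at a quarter of full titration and 38–99% at half. The upper ends move with how participant-by-strength variation is modelled.

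**Why log volume.** Suppose full titration and the same 20% cannabis effect at both strengths. Set placebo volume to 100 at 5% and 168.6 at 3%.

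- Absolute contrast: (120 − 100) − (202.3 − 168.6) = 20 − 33.7 = −13.7, although the relative effect is identical.
- Log contrast: ln 1.2 − ln 1.2 = 0.

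In the same simulation model, an absolute-volume contrast is significant in 6–24% of trials for an equal 20% effect and 13–76% for an equal 50% effect. The log contrast stays near 5% throughout.

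**Power of the contrast.** If each product's active-minus-placebo log difference has unit SD and the two differences correlate at ρ, the contrast has SD √(2(1 − ρ)). For standardised effects of 0.5 and 0.3 the noncentrality is 0.2 × √40 / √(2(1 − ρ)).

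| Assumed ρ | Noncentrality | Power | Gap for 80% power |
|---|---|---|---|
| 0 | 0.89 | 14% | 0.64 |
| 0.3 | 1.07 | 18% | 0.54 |
| 0.5 | 1.26 | 23% | 0.45 |
| 0.7 | 1.63 | 36% | 0.35 |

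**Success rule.** Each two-sided 0.05 test carries 0.025 in the hypothesised direction. With no effect in any product and independent differences, the chance of at least one such result is 1 − 0.975³ = 7.3%. Simulation with n = 40 gives 6.3% at correlation 0.5 and 4.2% at 0.9. Requiring all three gives 1.1% or less over the same range. Holm gives 2.5% at correlation 0 and 1.5% at 0.9. At an assumed standardised effect of 0.5 in one product only, power for that product is 87% unadjusted and about 74% under Holm.

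**The case against.** On the strength comparison, the plan describes its test accurately and nowhere calls it modulation by cannabis. The question about dose and product stands in a Background sentence on gaps in the literature, and neither Section 2 nor the stated hypotheses include an interaction. This stands: the contrast belongs among the secondary analyses, and its absence does not undermine the primary analysis. It does not remove the gap. The protocol raises the question and collects the placebo sessions at both strengths, then plans no consumption analysis that uses them together.

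The titration remark in Section 6a is made to argue safety, not to predict volume, and the documents give no volume difference or SDs. This also stands, so the titration figures are illustrations only.

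On the success rule, testing each product and the Objective 1 wording ("subsequently influences self-administration patterns (time to first self-administration, amount consumed, puffing topography characteristics) of tobacco cigarettes or e-cigarettes") can be read as three product-specific questions, each validly tested at 0.05. In a mechanistic laboratory study with three visible tests that is defensible. But the plan does not say so, and the hypothesis in part a is worded as one.

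A reader might infer that the primary analysis has a demonstrated type I error inflation that makes adjustment obligatory. The documents do not support that. The 4–7% arises only if one significant product is taken as proof, which no text proposes, and it depends on a correlation that is not given.

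**Conclusion.** The concern holds in two parts of unequal weight. The main part rests on the text and simple algebra: the active-only 3% versus 5% test estimates a strength difference and cannot show that cannabis changes it. No planned consumption analysis compares the cannabis effect between strengths, or between cigarettes and e-cigarettes. The size of any THC-free strength difference is unknown. The 46% and 87%, and the titration ranges, follow from assumed values.

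A reader might also infer that significant active-only results would be false positives. They would not. They would be correct detections of a strength difference, and the risk lies in what is concluded from them.

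The lesser part is an unstated decision rule. Its cost is a directional error of about 4–7% against 2.5% if any one product is counted, and less than 2.5% if all three are required and no product responds. Both matters can be settled in the plan before unblinding.

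**What to change.** 1. Add a secondary paired cannabis-by-strength contrast from sessions 3, 4, 6 and 7: (log active − log placebo at 5%) − (log active − log placebo at 3%). Report it as a ratio of active/placebo volume ratios with a 95% confidence interval. Pre-specify how sessions with zero consumption are handled, since their log is undefined.

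2. Label the existing active-only 3% versus 5% test as a strength comparison.

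3. State the rule for the three primary tests before unblinding. One choice is that they are separate product-specific claims, each at 0.05, none of which alone supports the overall hypothesis. The other is that an overall claim uses a Holm-adjusted or pooled test.

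The cost is plan wording and one more secondary analysis, with no new sessions or participants. The contrast has low power, so a non-significant result must not be read as no difference; the interval should carry the interpretation. Holm, if chosen, lowers single-product power from 87% to about 74% in the case worked above. A pooled test has its own weakness: at correlation 0.5 its power is 24% if one product alone has an effect of 0.5.

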Baseline Assessments. Prior to drug administration, baseline subjective and cardiovascular assessments will be completed. Participants must meet baseline cardiovascular criteria (HR < 100bpm, SYS BP < 150mmHg, DIA BP < 90mmHg), before an intravenous catheter is placed. The Time-Line Follow-Back (TLFB) assessment will be conducted to record recent use of tobacco, drugs, and alcohol. Concomitant medications, including vitamins and herbal supplements, will be also recorded. Any changes in medication occurring between the screening assessment and experimental session will be reviewed by a study investigator and medical staff prior to cannabis administration to ensure the volunteer is still eligible to participate. We will also administer a brief battery of cognitive/psychomotor performance tasks (DSST, PASAT, and DRUID App). Prior controlled studies in our laboratory have demonstrated that performance on these tasks are sensitive to acute cannabis-induced impairment. As in our other recent studies (e.g., IRB00199386), performance scores obtained at baseline (prior to drug exposure) will be compared to those obtained 5 hours post-cannabis administration to ensure participants can be safely discharged from the study (see below).

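### The secondary models specify no adjustment for the baseline taken before cannabis in every session; adding it could gain precision on vital signs, craving and cognition

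*Combined protocol and SAP*

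**What the plan says.** The model is described in Study Statistics, item c: "Secondary analyses will be conducted using repeated-measures multiple regression to evaluate the effects of nicotine/tobacco product type" (four levels: none, cigarette, low- and high-nicotine e-cigarette) and "time as within-subjects factors on subjective drug effect ratings, cardiovascular effects, craving, and cognitive performance effects". It is limited to data collected "during sessions in which active (10mg or 25mg THC) cannabis was administered", that is, four of the seven sessions. No covariate or change score is named, the levels of time are not listed, and nothing says whether a product-by-time interaction is tested.

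The baselines are described in Section 4a. Under Baseline Assessments: "Prior to drug administration, baseline subjective and cardiovascular assessments will be completed", together with the three cognitive and psychomotor tasks. Under Study Measures, vital signs, the Drug Effect Questionnaire, the craving questionnaires, DSST, PASAT and DRUID each have one baseline and eight post-cannabis times, from about 5 to 360 minutes. The only uses stated for these baselines are operational: the vital-sign limits before a session proceeds, and the comparison of vital signs and task scores at discharge.

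**The concern.** A person's heart rate, craving or test performance can differ from one session day to another for reasons unrelated to the product assigned. That day-level variation does not cancel when two sessions of the same person are compared. If nothing in the model represents it, it stays in the error of every product contrast. A measurement taken before cannabis, on the same day and the same scale, is the natural covariate for it, and it is already being collected.

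Two things are at stake. The first is precision in the models that address the hypotheses in Study Statistics item b, about nicotine use added to active cannabis. The sample size gives no margin to rely on: "The proposed sample size of 40 study completers was estimated based on limited prior studies", by analogy with one study of 20 people, with no effect size, standard deviation or power stated. The second is that leaving baseline handling open lets the analyst choose among options with quite different efficiency, across many outcomes.

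**Working it through.** **Inputs from the documents.** There are 40 completers (item c). For the tests, "All hypothesis tests will be two-sided; α will be set at 0.05". Each session has one baseline and eight post-cannabis times (Section 4a), and four sessions enter the model (item c). The 40 cannot be reproduced, because no effect size, standard deviation, correlation or power is given.

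**Assumptions.** Unadjusted power is set at 80%. The correlation r is within-person: between the session baseline and the session's post-cannabis value, after stable differences between people are removed. It is not in the documents, so a range is shown.

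**Step 1, detectable effect without adjustment.** For a paired contrast with n = 40, the noncentral t gives a standardized difference of 0.454 for 80% power. The normal approximation is (1.960 + 0.842)/√40 = 0.443.

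**Step 2, adding the session baseline.** The variance of the contrast is multiplied by (1 − r²)(1 + 1/(n − 3)) = (1 − r²)(38/37), with n − 2 = 38 degrees of freedom. The factor 38/37 is the price of estimating one slope. For comparison, a simple change from baseline, with equal variances before and after, multiplies the variance by 2(1 − r).

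| r | Variance factor, covariate | Power, covariate | Power, change score |
|---|---|---|---|
| 0 | 1.027 | 78.9% | 50.9% |
| 0.1 | 1.017 | 79.3% | 55.1% |
| 0.2 | 0.986 | 80.5% | 60.1% |
| 0.3 | 0.935 | 82.5% | 65.8% |
| 0.5 | 0.770 | 89.1% | 80.0% |
| 0.7 | 0.524 | 97.2% | 95.1% |

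The variance reduction is therefore about 6.5%, 23% and 48% at r = 0.3, 0.5 and 0.7. Break-even is where (1 − r²)(38/37) = 1, so r² = 1/38 and r ≈ 0.16; below that the covariate costs slightly more than it returns. A change score is worse than no adjustment whenever r is below 0.5.

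**Step 3, four sessions with one pooled slope.** The slope then has 39 × 3 = 117 degrees of freedom, and the penalty falls to about 1 + 1/115. Simulated variance ratios, adjusted to unadjusted, were 1.01 at r = 0, 0.96 at r = 0.22, 0.75 at r = 0.49 and 0.56 at r = 0.67.

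**Step 4, baseline as a ninth level of time.** If the product main effect is tested over nine times, and the effect is constant over the eight post-cannabis times and zero at baseline, the estimated effect is 8/9 of its true size. As an illustration, take session SD 0.4, residual SD 0.6 and effect 0.3 (all assumed). Then r = 0.16/√((0.16 + 0.36)(0.16 + 0.36/8)) = 0.49.

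- Nine levels: standardized difference (0.3 × 8/9)/√(2(0.16 + 0.36/9)) = 0.422, power 0.74.
- Eight post-cannabis times, unadjusted: 0.3/√(2(0.16 + 0.36/8)) = 0.469, power 0.82.
- Eight post-cannabis times with the baseline covariate: power about 0.905.

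**The case against.** The strongest reply is that the statistical plan is silent, which is different from deciding against adjustment. A reader might infer that the plan rules out using the baseline, or that it enters baseline as a ninth level of time and so dilutes the product effect. The text supports neither. It names the effects to be evaluated and leaves the rest open. The 8/9 dilution needs both conditions: baseline as a level of time, and inference on the product main effect. With product-by-time contrasts against baseline, nothing is averaged away.

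The second reply is that the design already does most of the work: "Evaluation of pharmacodynamic drug effects using a within-subjects design reduces variability across dose administration sessions". This stands. A high raw correlation between baseline and later values would not show a large loss, because it mostly reflects differences between people that the crossover removes. In simulation the raw correlation was about 0.88 to 0.92 whether the within-person r was 0 or 0.8. The standardized cigarette and breakfast (Section 4a, Experimental Session Procedures) and the baseline vital-sign limits may also keep r low.

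Third, the calculations assume an effect constant over the eight times, while product use is self-paced and subjective effects are expected to fade by the last assessment. That stands as a caution about averaging over time. It affects adjusted and unadjusted analyses alike and is no argument against the covariate.

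What does not stand is that adjustment is mere preference. The loss at r = 0 is about one power point, against gains of 9 points at r = 0.5 and 17 at r = 0.7.

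**Conclusion.** The point holds as a gap in specification with a possible gain in efficiency. Baselines are collected in every session, and the secondary models state no adjustment for them. The size is conditional on r: nil or slightly negative below about 0.16, about 2.5 power points at 0.3, 9 at 0.5 and 17 at 0.7, starting from an assumed 80%. These figures rest on a paired contrast in 40 completers and a linear baseline effect. Little gain is expected for drug-effect items that sit near zero before cannabis.

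A reader might take the omission as a source of bias. It is not: session order is randomized, and the baseline precedes both cannabis and product access, so the unadjusted and adjusted product contrasts estimate the same quantity. The scope is the secondary analyses of the four active-cannabis sessions. The primary outcome, total inhaled volume, has no pre-cannabis counterpart in the plan and is unaffected.

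**What to change.** In Study Statistics, item c:

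- State that the eight post-cannabis times are the outcomes and that baseline is not a level of time.
- For vital signs, craving, DSST, PASAT and DRUID, add the session's own baseline as a covariate in two parts: the participant's mean baseline over the sessions in the model, and the session's deviation from that mean. The second part carries the gain; the split keeps differences between people from distorting its slope. Make it optional for drug-effect items near zero at baseline.
- Say whether product-by-time is tested and which contrast carries the inference.
- Do not substitute a simple change score, which loses power when r is below 0.5.

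The cost is an added term in the model statement and one estimated within-person slope per model, worth about one power point if r is near zero. No new data, visits or procedures are needed. The choice should be written down before treatment codes are opened.
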